4.4 Exclusion criteria

Patient will be excluded from the study if she/he meets any of the following criteria:

- Patient has initially resectable metastatic disease for which neoadjuvant therapy is deemed superfluous.
- Patient does not consent to biopsy sampling.
- Patient has metastatic disease to lungs as the sole site.
- Patient has untreated or symptomatic brain metastasis (patient must be symptom-free without the use of corticosteroids).
- Patient has experienced a period of less than 6 months since discontinuation of adjuvant oxaliplatin-containing chemotherapy.
- Patient is ineligible for full chemotherapy doses (100% doses) at start of study treatment.
- Patient has had radiation therapy against the only measurable lesion within 4 weeks of start of study treatment.
- Patient has a medical condition treated with anticoagulant medication that cannot be replaced by low molecular weight heparin during active study treatment.

- Patient has a nervous system disorder worse than CTCAE grade 1.
- Patient has any medical condition that will preclude him/her from cancer immune-modulating therapy, such as:
 - Active or chronic hepatitis B or hepatitis C.
 - Known history of human immunodeficiency virus or acquired immunodeficiency-related illnesses.
 - Diagnosis of immunodeficiency or medical condition requiring systemic steroids or other forms of immunosuppressive therapy.
 - Autoimmune disease that has required systemic therapy within the past 2 years.
 - Receipt of live attenuated vaccination within 30 days prior to study entry or within 30 days of receiving study therapy.
 - Active infection or chronic infection requiring chronic suppressive antibiotics.
 - Known history of previous diagnosis of tuberculosis.
- Patient with current or prior use of immunosuppressive medication within 28 days before the first dose of study therapy, with the exceptions of intranasal corticosteroids or systemic corticosteroids at physiological doses that do not exceed 10mg/day of prednisone or an equivalent corticosteroid.
- Patient has any medical condition or needs to use medication, as listed in the SmPC of each Investigational Medical Product (IMP), that will preclude him/her from receiving treatment with IMP, such as:
 - Pernicious anemia or anemias due to vitamin B₁₂ deficiency (SmPC-listed contraindications for folinic acid).

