## 2.2. Randomization

The patients will be block-randomized into treatment arms with ratio 1:1 following a computer-randomized allocation sequence. The blocks will be defined according to sidedness and (K)RAS/BRAF mutation status of the primary tumor (right-sided versus left-sided and (K)RAS/BRAF wild-type versus mutation). The allocation sequence will be generated by the web-based Viedoc system.

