### **4.2. Eligibility**

Eligible patients, with no upper age limit to recruit subjects reflecting population-based incidence rates, have previously untreated, unresectable metastatic colorectal MSS adenocarcinoma. Essential study inclusion criteria are age  $\geq 18$  years, measurable infradiaphragmatic (liver, peritoneal and/or nodal) metastatic manifestation(s) according to Response Evaluation Criteria in Solid Tumors version 1.1 (RECIST 1.1), and Eastern Cooperative Oncology Group performance status 0-1. In addition, C-reactive protein (CRP)  $<60$  mg/L is required at study entry. A period  $<6$  months since discontinuation of neoadjuvant or adjuvant oxaliplatin-containing chemotherapy and a history of autoimmune disease are main exclusion criteria. The complete list of inclusion and exclusion criteria can be found with the clinical trial registration (ClinicalTrials.gov Identifier: NCT03388190) and in the trial protocol.

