### 5. Analysis

#### 5.1. End point definitions

*Primary end point:* PFS; radiologic assessment every 8 weeks, according to the Response Evaluation Criteria in Solid Tumors (RECIST) and the RECIST consensus guideline for assessment of response to immune-modulating therapies, iRECIST.

*Secondary end points:*

Safety: incidence of adverse events (AE), as reported according to Common Terminology Criteria for Adverse Events (CTCAE) version 4.0 recorded on ongoing basis.

Tolerability: AE grading, as assessed by CTCAE v4.0 recorded on ongoing basis.

ORR: the percentage of patients with a confirmed complete response (CR) or partial response (PR).

DOR: the time from the first documentation of a CR or PR to disease progression.

SSCRR: the percentage of patients with a confirmed resection of metastatic disease with microscopically free margin (R0).

OS: the time from randomization to death of any cause.

QoL: assessment undertaken at study enrolment, completion of the active therapy of the first treatment sequence (after 16 weeks), and disease progression, using the consensus modules EORTC QLQ-C30, EORTC QLQ-CIPN20, and EQ-5D-5L.

*Tertiary end point:* Cost estimate; evaluation of the healthcare costs (relating to the sequencing procedures and administered medication) and health effects (quality-adjusted life years), expressed as incremental cost-effectiveness ratio, of the sequential therapy relative to the control group as comparator.

*Exploratory end points:* Various analyses will be undertaken for exploratory end points listed in 1.2.

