Tolerability. Summaries by trial arm will be produced to show the proportion of participants experiencing each grade of CTCAE toxicities overall and during each treatment cycle. For more detailed summaries, this information will also be broken down into the different types of toxicities.

QoL. This will be summarized for each treatment arm at study enrolment, completion of the active therapy of the first treatment sequence (after 16 weeks), and disease progression, using the consensus modules EORTC QLQ-C30, EORTC QLQ-CIPN20, and EQ-5D-5L. The data will be illustrated graphically and presented as mean scores with 95% CI at separate time points. The differences in QoL between two treatment arms throughout the study period will be assessed by estimating a linear mixed model with fixed effects for time and treatment arm and the interaction between these two. Random effects for patients will be included. A significant interaction will quantify differences between the groups and serve as an omnibus test.

Safety and tolerability in the treatment arms will be compared by  $\chi^2$  or Fisher's exact test, as appropriate.

ORR is defined as the percentage of patients with a confirmed CR or PR. The proportion of participants achieving at least PR will be summarized with corresponding 95% CI for each treatment arm. The difference between the trial arms in the proportion of participants achieving at least PR will also be presented with corresponding 95% CI. The difference between participants achieving at least PR and remaining participants will be assessed using logistic regression adjusting for treatment group and stratification factors. Odds ratios with corresponding 95% CI and p-values will be presented for all variables incorporated in the model.

SSCRR is defined as the percentage of patients with a confirmed resection of metastatic disease with microscopically free margin (R0). Corresponding analyses as those to be performed for ORR will be applied for SSCRR.

DOR is defined as the time from the first documentation of CR/iCR or PR/iPR to disease progression. DOR Kaplan-Meier curves will be drawn and compared by log-rank test. The median DOR with corresponding 95% CI will be presented by treatment group. Stratified analyses will be performed as well. The Cox proportional hazards model, adjusting for the stratification factors, will also be used to compare DOR

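### SSCRR inherits the ORR logistic regression with no sparse-event method; if few patients are resected, the model's odds ratio, interval and p-value can be unusable

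*SAP*

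**What the plan says.** SAP 5.2 (Analysis methods) and protocol 10.4.5 (Secondary analyses) define SSCRR as the percentage of patients with a confirmed R0 resection of metastatic disease, and then state: "Corresponding analyses as those to be performed for ORR will be applied for SSCRR".

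The ORR analyses have three parts: the proportion per arm with a 95% CI, the difference between arms with a 95% CI, and a comparison that "will be assessed using logistic regression adjusting for treatment group and stratification factors". For the last part, "Odds ratios with corresponding 95% CI and p-values will be presented for all variables incorporated in the model".

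The stratification factors in SAP 2.2 are two binary variables ("right-sided versus left-sided and (K)RAS/BRAF wild-type versus mutation"). Entered as main effects with treatment, they give three covariates.

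No interval method is named for the proportions or the difference, and no exact or penalised model is named for SSCRR. The same section does offer Fisher's exact test where appropriate, but only for safety and tolerability. A general sentence near the end of SAP 5.2 says that methods will be adjusted if their assumptions are not met.

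**The concern.** Ordinary logistic regression has no finite maximum-likelihood estimate when the outcome is separated by a covariate, for example when one arm, or one level of sidedness or mutation status, has no events. Software then prints a very large coefficient with an enormous standard error, and the Wald p-value drifts towards 1 however one-sided the split is. The regression is the only source of a between-arm p-value for SSCRR. In that situation the plan has no usable test, and the replacement would be chosen after seeing which arm had the resections.

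**Working it through.** **Inputs from the documents.** There are 100 patients, 50 per arm (SAP 2.3). About 5% are expected to be excluded as non-MSS (SAP 3.3), which leaves about 95. The significance level is 5% (SAP 3.1). No SSCRR rate, event count or power is stated.

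**The plan's own figure.** The only figure to reproduce is the PFS sample size, which fixes n here. Freedman's formula at HR 0.5, two-sided 5% and 80% power gives (1.96 + 0.84)² × (1.5/0.5)² ≈ 71 events. Then 71/0.9 ≈ 79 patients, or 40 per arm, and 80 × 1.05 × 1.2 = 100.8. This agrees with the stated 40 per arm and 100 in total.

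**Assumptions.** The resection rate p is varied over 2–20% and is equal in the two arms unless stated. Right-sided tumours are taken as 30–50% and mutated tumours as 50–80%.

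**Treatment odds ratio.** It is not finite when at least one arm has no events. With m per arm, the probability is 1 − [1 − (1 − p)^m]². At p = 5% and m = 50: 0.95^50 = 0.077, and 1 − 0.923² = 0.148. With arms of 48 and 47, the same calculation gives 0.167.

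**Any of the three odds ratios.** This was simulated with N = 95 and 100, treatment balanced within strata, and 2,000–3,000 runs per scenario. Complete or quasi-complete separation was detected by linear programming.

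| Assumed rate | Treatment OR not finite (exact, 50 per arm) | At least one of three ORs not finite (simulated) |
|---|---|---|
| 2% | 60% | 79–88% |
| 3% | 39% | 58–79% |
| 5% | 15% | 30–57% |
| 8% | 3% | 9–31% |
| 10% | 1% | 3–19% |
| 15% | 0.06% | 0.3–7% |
| 20% | below 0.01% | 0–2% |

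With 48 and 47 analysed, the middle column becomes 42% at 3%, 17% at 5%, 4% at 8% and 1% at 10%. With unequal arms (simulated), 2% versus 6% gives a non-finite treatment OR in 38–43% of trials, and 5% versus 10% in 8–10%.

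**What would be reported, example 1: 6/48 versus 0/47.** Fisher's exact p is 0.026. The ordinary fit diverges: the treatment coefficient grows by about 1 per iteration, and after about 20 iterations the standard error exceeds 3,500 and the Wald p is about 0.996.

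**Example 2: 4/50 versus 0/50.** The ordinary OR is infinite. The possible replacements disagree:
- Fisher's exact p is 0.12.
- The Newcombe 95% CI for the difference is −0.6% to 18.8%.
- A score (Miettinen-Nurminen type) interval is 0.5% to 18.9%.
- The unadjusted likelihood-ratio statistic is 2 × {[4 ln 0.08 + 46 ln 0.92] − [4 ln 0.04 + 96 ln 0.96]} = 2 × (−13.94 + 16.79) ≈ 5.7 on 1 df, p ≈ 0.017.
- The Firth OR, with one right-sided event among the four, is 9.5 (95% CI 0.98 to 1260).

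At the 5% level the conclusion depends on which replacement is chosen.

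**Does the proposed model work?** Firth regression with a profile-likelihood interval gave a finite treatment OR and interval in 400 of 400 simulated trials at each of 2%, 5% and 10%.

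**The case against.** Several points on the other side are correct.

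- **Rarity is not documented.** A reader might infer from SAP 4.2, where eligible patients "have previously untreated, unresectable metastatic colorectal MSS adenocarcinoma", that resections are expected to be rare. The documents do not say so. Protocol 4.4 excludes only a patient who fits this description: "Patient has initially resectable metastatic disease for which neoadjuvant therapy is deemed superfluous". Resectable disease that needs neoadjuvant therapy is not excluded by that criterion. The safety committee's counting of curative resections (SAP 2.5) does not settle it either, because grade 3–5 toxicity is counted in the same sentence.
- **A one-sided result would not go unreported.** A reader might infer that the plan cannot report several resections in one arm and none in the other. It can: the per-arm proportions and the risk difference are already planned. Only the model's output fails, although a simple Wald interval for the proportion in an arm with no events would also collapse to zero width.
- **The text says only logistic regression.** It does not specify maximum likelihood or Wald tests. A Firth or exact fit would be consistent with it, and the general sentence on unmet assumptions would permit one. But nothing commits to such a fit, and example 2 shows that the choice can change the conclusion.
- **A non-finite stratum odds ratio does not by itself spoil the treatment odds ratio.** The right-hand column of the table therefore concerns the promise to report every variable, and the middle column concerns the arm comparison.
- **The fix adds no power.** With 50 per arm, Fisher's p is 0.24 for 0 versus 3, 0.12 for 0 versus 4 and 0.056 for 0 versus 5. With five events or fewer, even a complete split is not significant at 5%.

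**Conclusion.** The point holds as a conditional one. SAP 5.2 and protocol 10.4.5 prescribe the ORR regression for SSCRR and name no method for few events. If the resection rate is about 3% or lower, the treatment odds ratio is not finite in roughly 40–60% of trials. At 5% this falls to 15–17%, and from 10% upwards it is about 1% or less. The promise of an odds ratio for every variable fails more often: 30–57% at 5% and 3–19% at 10%. These figures rest on assumed rates and stratum prevalences, because the documents give neither.

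The documents do not support the stronger readings that resections are expected to be rare or that a one-sided result would be lost. What is lost in that case is the model's odds ratio, interval and Wald p-value, and with them the only planned test for SSCRR. This is a free improvement to a secondary end point. The primary PFS analysis is not affected.

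**What to change.** Replace the carry-over sentence for SSCRR in SAP 5.2 and protocol 10.4.5 with one that names:

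- for the risk difference already planned, a Newcombe or a Miettinen-Nurminen 95% CI, with one of the two chosen now because they can disagree at small counts;
- Fisher's exact test for the comparison between arms;
- Firth-penalised logistic regression on treatment and the two stratification factors, with profile-likelihood 95% CIs, for the adjusted odds ratio.

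Leave the ORR model as it is. If resections turn out to be common, little is lost.

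The cost is one sentence in each document, with no extra patients or data. The methods are available in SAS and Stata, both listed in SAP 5.6. Protocol 10.4.1 allows changes to the plan until database lock, and the change should be made before anyone sees resection counts by arm.

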2 STUDY OBJECTIVES AND END POINTS

Hypothesis: Most patients with metastatic CRC harbor tumor that can be transformed into an immunogenic disease by oxaliplatin, and may thereby benefit from the addition of immune-modulating therapy to improve outcome of the current oxaliplatin-based standard-of-care.

	Objectives	End points
Primary	
To determine PFS, in terms of failure of treatment strategy, on sequential treatment with the Nordic FLOX regimen and nivolumab² compared with the standard-of-care Nordic FLOX regimen in previously untreated MSS metastatic CRC.
 
² Nivolumab is an ICB agent.
	
 – PFS: radiologic assessment every 8 weeks (following 4 cycles of FLOX or the alternative 2 cycles each of FLOX and nivolumab), according to the Response Evaluation Criteria in Solid Tumors (RECIST) and the RECIST consensus guideline for assessment of response to immune-modulating therapies, iRECIST (c.f., Appendices 1 and 2).
Secondary	
To determine safety and tolerability of sequential treatment with the Nordic FLOX regimen and nivolumab compared with the standard-of-care Nordic FLOX regimen.
 
To determine objective response rate (ORR), duration of response (DOR), secondary surgical curative resection rate (SSCRR), and OS.
	
 – Safety: incidence of adverse events (AE), as reported according to Common Terminology Criteria for Adverse Events (CTCAE) version 4.0 (c.f., Appendix 3) recorded on onboing basis, and summarized every 4 weeks on active study therapy and every 8 weeks in planned breaks from active study therapy. – Tolerability: AE grading, as assessed by CTCAE v4.0 recorded on onboing basis, and summarized every 4 weeks on active study therapy and every 8 weeks in planned breaks from active study therapy. – ORR: the percentage of patients with a confirmed complete or partial response. – DOR: the time from the first documentation of a complete or partial response to disease progression. – SSCRR: the percentage of patients with a confirmed resection of metastatic disease with microscopically free margin (R0). – OS: the time from randomization to death of any cause.

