7.6 Tumor imaging and assessment of disease procedures

7.6.1 Evaluation of efficacy

The imaging assessments will be performed by CT, typically a thoracic/abdominal/pelvic CT scan. Tumor treatment response will be assessed according to RECIST v1.1 as the primary method and iRECIST as the secondary method. After baseline tumor assessments, evaluation of tumor response will be performed every 8 weeks (± 7 days). Additional MR scans or other radiologic evaluations will be performed if indicated.

All radiologic examinations will be transmitted to Study Radiologist at Akershus University Hospital within 1 working day after the scan is performed. A radiologist at the actual study center will evaluate the images for incidental findings that may have a therapeutic consequence (e.g., pulmonary embolism, immune therapy-related findings that require emergency actions).

Study Radiologist will be blinded to patient treatment, but will be informed about treatment breaks in the go-and-stop schedule. Study Radiologist will primarily assess tumor measures according to RECIST v1.1. If disease progression is concluded by means of RECIST v1.1, Study Radiologist will also assess tumor measures according to iRECIST. The radiology report will detail the criteria used for Clinical Investigator to make a decision about further study treatment (*c.f.*, [Paragraph 5.7.2.4](#)).

PFS will be calculated from the day of randomization to first recorded disease progression according to RECIST v1.1 or iRECIST when applicable, or death. Patients who have not had disease progression at the time of final analysis will be censored at the date last known to be alive and progression-free.

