7.6.7 Reporting of tumor response

All patients included in the study must be assessed for response to treatment, even if there is a major protocol treatment deviation or if they are ineligible, or not followed/re-evaluated. Each patient will be assigned one of the following categories: CR/iCR, PR/iPR, SD/iSD, PD/iCPD, early death from malignant disease, early death from toxicity, or early death from other cause or unknown (not assessable, insufficient data).

Early death is defined as any death occurring <30 days after randomization. Clinical Investigator will decide if the cause of death is malignant disease, toxicity, or other.

Patients for whom response is not confirmed will be classified as *Unknown*, unless they meet the criteria for SD/iSD (or the criteria for PR/iPR in case of an unconfirmed CR/iCR). Patients' response will also be classified as *Unknown* if insufficient data were collected to allow evaluation per these criteria.

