Appendix 2 – RECIST for immune-modulating therapies (iRECIST)

Comparison of RECIST v1.1 and iRECIST:

	RECIST 1.1	iRECIST
Definitions of measurable and non-measurable disease; numbers and site of target disease	Measurable lesions are ≥ 10 mm in diameter (≥ 15 mm for nodal lesions); maximum of five lesions (two per organ); all other disease is considered non-target (must be ≥ 10 mm in short axis for nodal disease)	No change from RECIST 1.1; however, new lesions are assessed as per RECIST 1.1 but are recorded separately on the case report form (but not included in the sum of lesions for target lesions identified at baseline)
Complete response, partial response, or stable disease	Cannot have met criteria for progression before complete response, partial response, or stable disease	Can have had iUPD (one or more instances), but not iCPD, before iCR, iPR, or iSD
Confirmation of complete response or partial response	Only required for non-randomised trials	As per RECIST 1.1
Confirmation of stable disease	Not required	As per RECIST 1.1
New lesions	Result in progression; recorded but not measured	Results in iUPD but iCPD is only assigned on the basis of this category if at next assessment additional new lesions appear or an increase in size of new lesions is seen (≥ 5 mm for sum of new lesion target or any increase in new lesion non-target); the appearance of new lesions when none have previously been recorded, can also confirm iCPD
Independent blinded review and central collection of scans	Recommended in some circumstances—eg, in some trials with progression-based endpoints planned for marketing approval	Collection of scans (but not independent review) recommended for all trials
Confirmation of progression	Not required (unless equivocal)	Required
Consideration of clinical status	Not included in assessment	Clinical stability is considered when deciding whether treatment is continued after iUPD

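### ORR and DOR do not share one response definition, and the DOR wording in SAP 5.2 can admit experimental-arm responders whom ORR excludes

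*SAP*

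**What the plan says.** **ORR.** SAP 5.2 gives "ORR is defined as the percentage of patients with a confirmed CR or PR". SAP 5.1, protocol chapter 2 and protocol 10.4.5 agree. None of them mentions iCR or iPR.

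**DOR, analysis text.** SAP 5.2, and protocol 10.4.5 in the same terms: "DOR is defined as the time from the first documentation of CR/iCR or PR/iPR to disease progression".

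**DOR, end point text.** SAP 5.1: "DOR: the time from the first documentation of a CR or PR to disease progression". Protocol chapter 2: "DOR: the time from the first documentation of a complete or partial response to disease progression". None of the four DOR definitions contains the word confirmed.

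**Response duration.** Protocol 7.6.8 counts it from randomization.

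**Where iRECIST applies.** Protocol 7.6.4 describes its use in the experimental arm. Protocol 7.6.6 dates progression at RECIST PD in the control arm and at iCPD in the experimental arm. Protocol 7.6.1 names RECIST v1.1 as the primary method and sets no arm limit on the iRECIST reading: "If disease progression is concluded by means of RECIST v1.1, Study Radiologist will also assess tumor measures according to iRECIST". The radiologist is blinded to treatment.

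**Response after progression.** For RECIST 1.1, Appendix 2 says: "Cannot have met criteria for progression before complete response, partial response, or stable disease". For iRECIST it allows iCR or iPR after iUPD, but not after iCPD.

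**Reporting.** Protocol 7.6.7 pairs the two systems: "Each patient will be assigned one of the following categories: CR/iCR, PR/iPR, SD/iSD, PD/iCPD".

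**The concern.** DOR describes how long the responders counted in ORR stay in response, so the two end points should rest on the same patients. Here the analysis text for DOR is wider than the text for ORR, and it conflicts with the SAP's own end point section. A programmer cannot derive a single DOR variable from these passages.

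The difference may also depend on arm. If iRECIST is scored only in the experimental arm, only that arm can contribute a first response reached after RECIST progression. Both end points are compared between arms: DOR by Kaplan-Meier curves, log-rank test and Cox model, and ORR by a difference with its 95% CI and by logistic regression. DOR uses responders only, in arms of 50, so a few patients admitted under a different rule can shift the experimental curve and median. Separately, the end of DOR depends on arm if 7.6.6 governs it: the same growth ends a response at RECIST PD in the control arm, but only at iCPD in the experimental arm. Protocol 7.6.4 places the confirming assessment 4 to 8 weeks later.

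**Working it through.** The plan gives no response rate, sample size or power for ORR or DOR, so there is no figure to reproduce. The check compares the texts.

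**Step 1: one scan history, scored in each arm.** Take a patient with stable disease who then meets RECIST PD. Under iRECIST this is iUPD. The next assessment does not confirm iCPD. The tumor then shrinks at least 30% from baseline, and this holds at least 8 weeks later, as 7.6.3 and 7.6.4 require before a response is claimed.

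- By RECIST v1.1 as set out in Appendix 2, this patient cannot be a PR, because progression came first.
- By iRECIST (7.6.4 and Appendix 2), this patient is an iPR, because only iUPD came first.

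**Step 2: apply each combination of the definitions.**

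| Reading | Experimental: ORR / DOR | Control: ORR / DOR |
|---|---|---|
| A. ORR as worded, DOR per SAP 5.2, iRECIST in experimental arm only | no / yes | no / no |
| B. ORR as worded, DOR per SAP 5.1 | no / no | no / no |
| C. ORR from the paired 7.6.7 categories, DOR per SAP 5.2, iRECIST in experimental arm only | yes / yes | no / no |
| D. ORR as worded, DOR per SAP 5.2, iRECIST in both arms (7.6.1) | no / yes | no / yes |
| E. ORR from the paired 7.6.7 categories, DOR per SAP 5.2, iRECIST in both arms | yes / yes | yes / yes |

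The ORR and DOR sets differ under A and D. The arms are scored by different rules under A and C. Only B and E avoid both problems, and the documents do not choose between the five readings.

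**Step 3: who can be affected.** A patient with a confirmed RECIST response before any progression is already in both sets. A patient who reaches iCPD cannot later be iCR or iPR. That leaves patients with no earlier RECIST response, unconfirmed progression, and then a first iCR or iPR.

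**Step 4: scale, by assumption only.** Assume 50 experimental patients, a RECIST ORR of 30% to 60%, and k = 1 to 5 patients of the kind in Step 3. Neither the rates nor k comes from the documents.

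- ORR responders: 0.30 × 50 = 15 to 0.60 × 50 = 30.
- DOR set under reading A: 15 + 1 = 16 to 30 + 5 = 35.
- Share of the experimental DOR set that is not in ORR: from 1/(30 + 1) = 3% to 5/(15 + 5) = 25%.
- Rise in experimental ORR under reading C: from 1/50 = 2 to 5/50 = 10 percentage points.
- Under reading B all of these are zero.

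**The case against.** The strongest reply is that this is loose notation. The iRECIST table in 7.6.4 assigns iCR and iPR also where there has been no previous iUPD, so the labels can cover ordinary responses. The paired forms in 7.6.7 and in the DOR text may then be shorthand, with ORR merely abbreviated. That is possible, but 7.6.1 calls for the iRECIST reading after RECIST progression, so the texts do not settle it. If the shorthand was meant, ORR is scored by the looser rule in the experimental arm unless control scans are read the same way.

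The control side is not airtight either. Protocol 7.6.3 classifies best response up to the end of treatment, and control treatment continues after progression in a break (5.5). It could therefore be read to admit a PR after therapy restarts; the bar comes from Appendix 2. Protocol 7.6.1 has a blinded radiologist apply iRECIST with no arm limit. Arm dependence therefore rests on 7.6.4, 7.6.6 and Appendix 2.

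On confirmation, 7.6.3 and 7.6.4 require a second assessment before a response is claimed, which may imply it for DOR. Appendix 2 says that confirmation is needed only in non-randomised trials, so the DOR definition should say which applies.

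Finally, these are secondary end points in a phase 2 trial sized on PFS. That limits the weight of the point but does not remove the contradiction.

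**Conclusion.** The point holds as an unresolved conflict of definitions with a possible arm-dependent effect. DOR has two starting rules, plus a duration counted from randomization in 7.6.8. One of the starting rules does not match ORR. Followed literally, with iRECIST confined to the experimental arm, SAP 5.2 can put experimental patients into DOR who are not ORR responders.

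The number of such patients cannot be derived from the documents. The 3% to 25% range in the working shows scale under assumed inputs and is not an estimate.

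Three stronger readings are tempting and are not supported:

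- A reader might infer that ORR and DOR describe different patients however the plan is read. They match if DOR follows SAP 5.1, or if ORR uses the paired 7.6.7 categories.
- A reader might infer that any patient who progresses in a treatment break and shrinks after restart is an extra experimental responder. If progression has been confirmed as iCPD by then, Appendix 2 rules out a later iPR.
- A reader might take the three restarts of the average experimental patient in protocol 5.5, assume a first-sequence response of 40% to 50% and a 5% to 15% chance of first response per restart, and conclude that 7% to 23% of the arm is affected. Neither rate is in the documents. The calculation also gives three restarts to every first-sequence non-responder, including those who fail on therapy, die, withdraw or stop for toxicity, and it ignores iCPD.

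**What to change.** Make the same change in SAP 5.1, SAP 5.2, protocol chapter 2 and protocol 10.4.5:

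1. Define a responder, for both ORR and DOR and in both arms, as a confirmed CR or PR by RECIST v1.1, the primary method in 7.6.1.
2. Restrict DOR to those ORR responders.
3. End DOR by the same progression criterion in both arms, and say how this relates to 7.6.6.
4. Reconcile 7.6.8 with this definition, so that response duration does not start at randomization.
5. Tabulate the RECIST and iRECIST categories of 7.6.7 separately.
6. Report iRECIST response and its duration in a separate descriptive or sensitivity table, stating in which arms iRECIST was scored.

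Counting CR/iCR and PR/iPR for both end points would also align ORR with DOR, but would treat the arms alike only if iRECIST were scored in both. RECIST v1.1 avoids that condition.

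The cost is wording and one extra table. These are analysis definitions and do not alter treatment decisions. The small downside is that responses after pseudoprogression appear only in the iRECIST table. Protocol 10.4.1 allows changes to the statistical plan until database lock, so this should be settled before then.
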